Decrements in **cognitive performance** occur when core temperature increases by about 1°C (Reinersten et al., 2008; Simmons et al., 2008). The level of cognitive decline depends on exposure duration, the intensity and complexity of the activity, and— importantly— the degree of hyperthermia (Gaoua et al., 2011; Simmons et al., 2008). There have been several heat stress studies performed in industrial settings and in climatic heat chambers. Processing speed and reaction time, short-term memory, and decision are all impaired (Gaoua et al., 2011; Sun et al., 2012; Piil et al., 2017; Mazlomi et al., 2017).

Cooling the skin reduces the unpleasant sensations caused by excessive heat exposure (Simmons et al., 2008). Localized cooling of the torso during systemic heat exposure reduces physiological stress by lowering body skin and core temperatures, decreasing heart rate, reducing sweat rate, and improving perception of thermal comfort (Chang, Song, & Yang, 2015). **Cooling vests** worn under impervious surgical gowns serve as a heat sink and reduce unpleasant sensations and the symptoms of physiological stress (Smolander et al., 2004; Kenney et al., 2011; Reinersten et al., 2008).

We propose to test the primary hypothesis that **wearing a cooling vest during surgery improves surgeons' perception of thermal comfort**. Secondary, we will test the hypothesis that **wearing a cooling vest during surgery reduces surgeons' mean-body temperature and preserves their cognitive performance**.

Specific Aims

1. Our **primary aim** is to evaluate surgeons' self-rated thermal comfort with and without a cooling vest during prolonged and strenuous surgery.
Primary hypothesis: Surgeons' self-rated thermal comfort is improved by wearing a cooling vest during prolonged and strenuous surgery.
2. A **secondary aim** is to evaluate surgeons' mean-body temperature with and without a cooling vest during prolonged and strenuous surgery.

Secondary hypothesis 1: Surgeons' mean-body temperature, estimated from core and mean-skin temperature, is reduced by wearing a cooling vest during prolonged and strenuous surgery.

3. Another **secondary aim** is to evaluate surgeons' cognitive performance with and without a cooling vest just after prolonged and strenuous surgery.

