Primary Outcome will be self-rated thermal comfort. Immediately after surgery, *while still gowned*, surgeons will rate their thermal comfort on a 0-10 Likert scale, with 0 representing extreme cold, 5 being thermal comfort, and 10 representing extreme heat. Two points on the 11-point Likert scale will be considered a clinically important difference.

Secondary Outcome #1 - mean core temperature. The first secondary outcome will be the mean core temperature for a case, calculated as the time-weighted average over the taken measurements. The surgeon's core body temperature will be monitored by a validated wireless wearable iThermonitor WT701 biosensor which estimates core temperature within $\pm 0.5^{\circ}\text{C}$ (Pei et al., 2018). The sensor will be applied to the surgeon's right axilla 15-20 minutes prior to the surgical hand scrub performed at the start of surgery and secured with an adhesive cover. A small patch of axillary hair will be clipped or shaved as necessary. After the temperature sensors are applied, the surgeon's oral temperature will be measured by the Femometer adult digital oral thermometer which meets professional accuracy standards for digital thermometers (ASTM E1112-00) to support the accuracy of the iThermonitor core body temperature measurement. The surgeon's oral temperature will be measured for a second time when the surgeon exits the surgical field prior to taking the C3B battery assessment.

Secondary Outcome #2 - mean skin temperature. The second secondary outcome will be the mean skin temperature for a case, calculated as the time-weighted average over the taken measurements. Mean skin temperature will be estimated from skin temperature from the back of the upper chest, deltoid arm, thigh, and calf using the formula $[\text{MST}_R = 0.3 t_{\text{chest}} + 0.3 t_{\text{arm}} + 0.2 t_{\text{thigh}} + 0.2 t_{\text{leg}}$ or $0.3(t_{\text{chest}} + t_{\text{arm}}) + 0.2(t_{\text{thigh}} + 0.2 t_{\text{leg}})]$ (Ramanathan, 1964). Skin temperature will be continuously measured using wireless patches, TempTraq, which meet professional accuracy standards for digital thermometers (ASTM E1112-00). The sensors will remain affixed with adhesive dressing on the surgeon's body surface throughout surgery and approximately 10 minutes required for post-operative testing.

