Participants' age, weight, height, and other continuous demographics and baseline characteristics will be summarized using descriptive statistics (n, mean, median, standard deviation, minimum and maximum), while race, surgical specialty, as well as other categorical variables will be summarized with frequency tabulations. The 4 sequence groups will be compared on baseline variables descriptively.

Specific Aim 1) Evaluate the difference between surgeons' self-rated thermal comfort with and without a cooling vest during prolonged and strenuous surgery. 0-10.

Perceived measure of thermal comfort for both conditions, with and without a cooling vest will be analyzed by descriptive statistics recommended for ordinal Likert scale items – i.e., frequencies and median [quartiles].

We will use a linear mixed effects model to test the treatment effect of the cooling vest on mean thermal comfort. We will adjust for treatment, sequence and period effects, and include subject as a random effect to account for the within-subject correlation. We will test for differential carryover effect by assessing the treatment-by-period interaction. If no interaction is detected the interaction term will be removed and the treatment effect assessed in a main effects model.

Specific Aim 2) Evaluate the difference between the surgeons' core, mean skin, and mean body temperatures with and without a cooling vest during a prolonged strenuous surgery.

For each temperature we will used a linear mixed effects model to test the treatment effect of the cooling vest on a subject's temperature during the case. We will adjust for treatment, sequence and period effects, and include subject as a random effect to account for the within-subject correlation. We will test for differential carryover effect by assessing the treatment-by-period interaction. If no interaction is detected the interaction term will be removed and the treatment effect assessed in a main effects model.

Specific Aim 3: Evaluate the difference between the surgeons' measure of cognitive performance with and without a cooling vest just after a prolonged strenuous surgery.

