Cognitive performance will be measured by the C3B performance-based battery of cognitive tests at the end of the case. An overall score for a subject after a particular case will be calculated by first rescaling (e.g., so that each item ranges from 0 to 100) and then averaging the scores across the battery. Treatment effect will be assessed using a linear mixed effects model as described for Aims 1 and 2.

The significance level will be 0.05 for the primary outcome (Aim 1) and 0.05 across the 3 secondary outcomes (2 temperatures, cognitive function), such that the secondary outcomes will be assessed at a significance criterion of $0.05/3=0.017$. SAS statistical software version 9.4, Carey, NC, will be used for all analyses.

Specific Aim 4: Evaluate the difference between the surgeons' perceived ergonomic workload with and without a cooling vest during a prolonged and strenuous surgery.

Perceived ergonomic workload will be measured by duration of the surgical procedure recorded in minutes, surgeons' report of the number of hours slept prior to the study day, Borgs' visual analog scale for exertion (0-10), and the Rating of fatigue scale (0-10).

Perceived ergonomic workload for both conditions, with and without a cooling vest will be analyzed by descriptive statistics recommended for ordinal measured items – i.e., frequencies and median [quartiles].

We will use a linear mixed effects model to test the treatment effect of the cooling vest on mean perceived levels of exertion and fatigue. We will adjust for treatment, sequence and period effects, and include subject as a random effect to account for the within-subject correlation. We will test for differential carryover effect by assessing the treatment-by-period interaction. If no interaction is detected the interaction term will be removed and the treatment effect assessed in a main effects model.

Sample Size Justification.

Sample size calculation is based on having 90% power at the 0.05 significance level to detect a difference of 2 or more (on a scale of 0-10) on surgeons' self-rated thermal comfort with and without a cooling vest. With an estimate SD (s) of 3 for thermal comfort in each group, and an assumed within-subject correlation (ρ) of 0.5, the estimated SD of the within-subject difference would be

$$\sqrt{s_1^2 + s_2^2 - 2\rho s_1 s_2}, \text{ or } \sqrt{2(3^2) - 2(0.5)(3)(3)} = 3.$$

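### Secondary hypothesis 1 concerns mean-body temperature, which has a planned model but no combining weight, no outcome number and no clear share of the secondary alpha

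*Combined protocol and SAP*

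**What the plan says.** Four places in the combined protocol and SAP describe the temperature endpoint.

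- **Specific Aims.** The second aim "is to evaluate surgeons' mean-body temperature with and without a cooling vest during prolonged and strenuous surgery". Its hypothesis is that "Surgeons' mean-body temperature, estimated from core and mean-skin temperature, is reduced by wearing a cooling vest during prolonged and strenuous surgery". This is one quantity; its two inputs are named, but not how they are combined.
- **Measurements.** Outcome #1: "The first secondary outcome will be the mean core temperature for a case, calculated as the time-weighted average over the taken measurements". Outcome #2: "The second secondary outcome will be the mean skin temperature for a case, calculated as the time-weighted average over the taken measurements". Mean skin has an explicit four-site weighting formula. Mean-body temperature is not a numbered outcome and has no formula.
- **Data Analysis, Specific Aim 2.** The task is to "Evaluate the difference between the surgeons' core, mean skin, and mean body temperatures with and without a cooling vest during a prolonged strenuous surgery", and "For each temperature we will used a linear mixed effects model to test the treatment effect of the cooling vest". Three temperatures are modelled.
- **Data Analysis, significance level.** The secondary level is "0.05 across the 3 secondary outcomes (2 temperatures, cognitive function"), so each test is made at 0.05/3, rounded in the plan to 0.017.

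**The concern.** The quantity named in the hypothesis is not one of the outcomes that the plan defines, and it is not clearly one of the tests that receive alpha. Three things are left open.

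- **The weight.** Mean-body temperature is w × core + (1 − w) × mean skin for some w. Without a stated w, the variable is fixed only when someone calculates it. A value chosen after the data are seen would be hard to defend.
- **The alpha.** Three temperatures are modelled and two are counted. The mean-body test is either a fourth test beside core, skin and cognition, or it replaces one of the counted temperatures. The text does not say which.
- **Disagreement.** If mean skin falls and core does not, the two numbered outcomes give one positive and one negative result. No rule says what follows for hypothesis 1. This is a realistic pattern for a vest with frozen packs on the shoulders, flanks and mid-back.

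At stake is whether the trial can make a clean statement about its only temperature hypothesis.

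**Working it through.** **1. The plan's own figures reproduce.** SD of the difference = √(2 × 9 − 2 × 0.5 × 9) = 3, so d = 2/3. A two-sided paired t test at 0.05 (the plan does not state sidedness) needs 26 subjects for 90% power (power 0.904 at 26). With 26 subjects and alpha 0.05/3, the effect detectable with 90% power is 0.766, or 0.764 at the rounded 0.017. The plan states 0.76. The sample-size arithmetic is sound.

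**2. Alpha.** Core, mean skin, mean body and cognition, each at 0.05/3, give a Bonferroni bound of 4 × 0.05/3 = 0.067, against 0.05 planned. If the four tests were independent, the figure would be 1 − (1 − 0.05/3)⁴ = 0.065. Mean body is built from core and skin, so the tests are not independent; 0.067 is an upper limit.

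**3. The weight.** The documents give no temperature SDs, effects or weights. All of these are assumptions:
- within-surgeon case-to-case SD of 0.3 °C core and 0.7 °C mean skin, independent of each other;
- 26 surgeons with two cases per condition (52 against 52);
- 104 − 26 − 3 − 1 = 74 degrees of freedom;
- two-sided alpha 0.05/3;
- core weight w from 0.6 to 0.9.

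Formulas: effect = w × core effect + (1 − w) × skin effect; SD = √(w² × 0.3² + (1 − w)² × 0.7²); SE = SD × √(2/52); power from the noncentral t. At w = 0.9, for example, SD = √(0.0729 + 0.0049) = 0.279 and SE = 0.055.

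| Core, skin effect (°C) | w = 0.6 | w = 0.7 | w = 0.8 | w = 0.9 |
|---|---|---|---|---|
| 0, −1.0: mean-body effect | −0.40 | −0.30 | −0.20 | −0.10 |
| 0, −1.0: power | about 100% | 99.6% | 89% | 27% |
| −0.1, −1.0: power | about 100% | about 100% | 99.6% | 84% |
| 0, −0.5: power | 73% | 55% | 28% | 7% |
| −0.1, −0.5: power | 93% | 90% | 80% | 55% |

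**4. Core and skin read separately.** With core 0 and skin −1.0 °C, the skin test is positive about 100% of the time and the core test 1.7%. With core −0.1 °C, the core test has 23% power. The numbered outcomes would therefore often split in these cases.

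**The case against.** A reader might infer that the plan never tests the hypothesis. It does not support that: Data Analysis names mean-body temperature under Aim 2 and plans a mixed model for each temperature. The natural reading is that this model answers the mean-body hypothesis, with core and skin as its components. The inputs are named and each has a measurement method and time-averaging rule. This stands. What it leaves open is the weight, the outcome listing and the alpha.

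Methods also promises a complete analysis plan ahead of any look at the data, and a weight is the kind of detail such a plan can settle. So the gap can still be closed. The combined document supplied does not close it, and the mismatch between three modelled and two counted temperatures is a conflict in the text rather than a detail deferred.

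The power figures rest on assumptions. The Introduction expects torso cooling to lower both skin and core temperature. When both fall, the weight matters less, as the rows with core −0.1 °C show. Independence of core and skin is also assumed: at a residual correlation of 0.5, the 73% becomes 54%. These points stand and limit the size of the claim. They do not supply a rule for the case where core and skin diverge.

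**Conclusion.** The hypothesised quantity has a planned model, but no combining weight, no outcome number and no clear place in the three-test family. If it is tested in addition to the three counted outcomes at 0.05/3, the family error can reach 0.067. If core and skin stand in for it, nothing covers the case where they disagree.

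The effect of the weight is conditional. Under the assumptions above it moves power from about 100% to 27% when only skin falls (by 1.0 °C), and leaves it at 84% or more when core falls 0.1 °C as well.

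A reader might infer that the same data could yield opposite conclusions. The cases shown do not support that: every mean-body effect in them is a reduction, and non-significance at a high core weight is lost power, not evidence of the contrary. A change of sign needs core to rise. With core +0.2 °C and skin −0.5 °C it occurs at w = 0.5/0.7 = 0.71, but the documents give no ground for expecting such a rise.

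The point concerns one secondary hypothesis. The primary outcome and n = 26 are unaffected.

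**What to change.** Before any data are evaluated, choose one of two routes and make the four places agree.

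(a) **Keep the mean-body hypothesis.** Add mean-body temperature to Measurements as a numbered outcome, w × core + (1 − w) × mean skin, with one sourced value of w, calculated at common time points and time-averaged over the case. State under Specific Aim 2 in Data Analysis that it decides hypothesis 1, with core and mean skin reported as components so that a skin-only effect is visible. Make it the temperature test in the secondary family and restate the divisor and detectable effect. With cognition, that is two tests at 0.025 and a detectable effect of 0.73 at 26 subjects and 90% power.

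(b) **Keep the two temperatures.** Reword Aim 2 and hypothesis 1 to core and mean skin temperature, drop mean-body temperature from Data Analysis, keep the three-test family at 0.05/3, and limit the claim to the temperature or temperatures that pass their own test.

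Either route is a change of wording; both inputs are already recorded. Under (a), core and skin become supporting results. Under (b), the mean-body claim is given up.

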Surgeon research subjects will be recruited by posting information about the study on the Orthopedic and Rheumatology Institute website. All human subject research protocols instituted by the Cleveland Clinic will be followed and documented. Participating surgeons will be advised of all known risks and benefits of study as well as information describing the requirements of the study and data management. The surgeons will be advised of the option to stop participation at any time. Written informed consent will be obtained from each surgeon.

Participating surgeons will be assigned a study number and only this number will be included on case-report forms. A single cross-linking record will identify specific surgeons for the purpose of organizing cross-over cases. Otherwise, analysis will be based on study number and no individual data will be linked to specific surgeons. Case-report forms will be kept locked in a secure research office and data-acquisition iPads will be encrypted.

We do not plan to obtain consent from patients for this comparative effectiveness trial that evaluates an FDA exempt device designed to improve *surgeons' comfort*.

Protocol

We propose a randomized cross-over trial using a uniform and strongly balanced 4-period design in which will include four operations for each surgeon. Surgeons will be randomized to 1 of 4 sequences: ABBA, BAAB, AABB or BBAA. The design is “uniform” in that each treatment appears the same number of times within each sequence (uniform within sequence) and if each treatment appears the same number of times within each period (uniform within each period). It is strongly balanced with respect to first-order carryover effects because each treatment precedes every other treatment, *including itself*, the same number of times.

We chose this design versus a parallel group design because 1) it removed the potential for confounding, even with a small sample size, as comparisons are made within subject, and not between subjects; 2) the design is very efficient since within-subject comparisons are correlated, obviating the need for a larger study which would also not be practical in this setting. Also, no differential carryover effect is expected in this study, removing one of the main concerns with crossover trials.

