Surgeons will be randomly assigned to use either the CoolSource™ cooling vest (worn between scrubs) and a conventional surgical gown for each of 4 surgeries. Sequence of treatments within surgeons will be randomized (ABBA, BAAB, AABB or BBAA), and determined using the PLAN procedure in SAS, such that each surgeon will wear vest and non-vest twice. The sequencing will not be shared with any study personnel. Allocation for each case will be concealed with a web-based system that will be accessed only shortly before surgery.

We will target an ambient temperature of $21^{\circ}\text{C} \pm 1^{\circ}\text{C}$, and try to maintain the same temperature of each of the four study cases for each surgeon. The CoolSource vest holds six reusable cooling packs

located bilaterally on the shoulders, angled flank along the base of the rib cage, and along each side of the spine, mid-back. The vest will be donned over hospital-issued scrubs after all temperature sensing devices have been applied and before surgical hand scrubbing. Surgeons will wear the vest throughout surgery, and for a few additional minutes while postoperative assessments are made (details below).

The weight of the disposable cooling vest is 1 kg which is evenly distributed over both shoulders. The cooling packs have an insulated cover to reduce condensation or sweating while seated inside the vest pocket. The flexible frozen reusable cooling packs will be inserted into each of the six pockets and the vest belt will be tied to hold the cooling packs securely. The disposable cooling vests will be discarded after each case, and the cooling packs returned to a freezer.

Measurements

A questionnaire detailing demographic information (age, height, weight, age, ethnicity, and education level) training level, specialty program, and estimated past case volume will be completed by participating surgeons before their first case.

Temperature of the freezer holding the cooling packs will be assessed before randomization to confirm that the temperature is <0°C.

Before every surgical case starts the time the surgeon dons the cooling vest and the time the surgeon dons the sterile surgical gown will be recorded.

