Secondary Outcome #3 will be surgeons' cognitive performance, measured with the C3B battery. The self-administered C3B is a performance-based battery of cognitive tests which measure visual memory; episodic learning and delayed memory (five learning trials with a total score of 70) and processing speed; information processing speed and incidental memory (15 symbols repeated for 120 seconds). Also, relevant distractions or interruptions (phone call, pager, staff, equipment, and other) will be recorded and the frequency in which they occur during the C3B battery test. Both tests will be aggregated using z-scores and summing the z-scores within patient. A greater than 10% within-subject difference in total scores will be considered significant. Testing will take place right after surgery with surgeons still gowned. The surgeons will sit with the iPad touch screen placed on a desk in front of them for approximately 10 minutes to complete the cognitive test. To minimize learning during the trial, participating surgeons will complete the cognitive assessment battery before the first study day. For subsequent cases, the test will be administered prior to the surgical hand scrub and after the end of surgery. The C3B test modules use auditory test instructions and on-screen visual test stimuli consistent with symbols, single digits, and single letters.

Secondary Outcome #4 will be surgeon' perceived ergonomic workload measured with Borg CR₁₀ scale of exertion and the rating-of-fatigue (ROF) scale.

Immediately after surgery, *while still gowned*, surgeons will rate their perceived exertion on a 1-10 Borg CR₁₀ scale, with 1 representing very slight exertion, 5 being severe, and 10 representing maximal exertion. Perceived fatigue will be rated on a 0-10 ROF scale, with 0 representing not fatigued at all, 5 moderately fatigued, and 10 total fatigue & exhaustion. Two points difference on either scale will be considered a clinically important difference. Time the surgeon removes the sterile surgical gown and the cooling vest after completing the C3B will be recorded. Also, total amount of time the surgeon wore the sterile surgical gown / cooling vest in minutes will be calculated.

Ambient operating room temperatures will be monitored at ≤15-minute intervals with an electronic thermometer positioned eight feet from the base of the OR table, outside of the surgical field on the circulating nurses' workstation.

Data Analysis

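### The crossover removes only stable surgeon characteristics; factors that may differ between a surgeon's four operations are left out of every model, which costs precision, and two of them are listed as workload measures

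*Combined protocol and SAP*

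**What the plan says.** Under Methods, Protocol, the first reason given for the crossover is that "it removed the potential for confounding, even with a small sample size, as comparisons are made within subject, and not between subjects".

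The same document accepts that the operation itself matters. The paragraph before the conceptual-framework figure names room temperature and the type and length of the procedure as contributors to surgeons' heat stress. Subject selection admits hip and knee arthroplasty and similar elective cases scheduled for 90 to 150 minutes, with no rule that a surgeon's four cases be the same procedure. The room is targeted at 21 °C ± 1 °C, and the team will "try to maintain the same temperature of each of the four study cases for each surgeon". Under Measurements, "Ambient operating room temperatures will be monitored at ≤15-minute intervals", but no use of these readings in the analysis is stated.

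For Aim 1 the model is: "We will adjust for treatment, sequence and period effects, and include subject as a random effect to account for the within-subject correlation". Aims 2 and 4 repeat this. For Aim 3, "Treatment effect will be assessed using a linear mixed effects model as described for Aims 1 and 2". The only further term is the treatment-by-period interaction.

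Under Measurements, Secondary Outcome #4 (perceived ergonomic workload) consists of the Borg CR10 exertion scale and the rating-of-fatigue scale. Under Data Analysis, Aim 4 adds procedure duration and "surgeons' report of the number of hours slept prior to the study day".

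**The concern.** Each period of this crossover is a different operation on a different patient. Surgeon-level factors such as age, fitness and habitual heat tolerance cancel in the vest contrast. Case-level factors do not, and the protocol itself names several of them as sources of heat load. Left out of the models, their effect stays in the residual, so every vest estimate is less precise than the planned data would allow. The rationale also tells the reader that nothing of this kind is left to handle.

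The Aim 4 list raises a second problem. Sleep is complete before the vest is put on and cannot respond to it. Case duration is not a perception. With both counted as workload measures, the outcome has two definitions in one document, and the planned descriptive summary of workload would mix outcomes with background variables.

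**Working it through.** **Inputs.** From Sample Size Justification: SD 3 in each condition, within-subject correlation 0.5, difference 2 points, power 90%, significance level 0.05 (taken as two-sided), 26 surgeons. From Protocol: four cases per surgeon, two with the vest and two without. Assumed, because the documents give no figure: the share R² of within-surgeon variance explained by case factors known before allocation, shown at 10%, 20% and 30%.

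**The plan's own figure.** SD of the difference = √(2×9 − 2×0.5×9) = 3. A paired t-test for a 2-point difference gives power 0.904 at n = 26 and 0.892 at n = 25. The stated 26 reproduces.

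**Standard error with four cases per surgeon.** That calculation counts one observation per condition; the design supplies two. With equal correlation among all four cases:
- residual variance = 9 × (1 − 0.5) = 4.5
- number of cases = 26 × 4 = 104
- SE of the vest effect = 2 × √(4.5/104) = 0.416
- residual df = 104 − 26 surgeons − 3 periods − 1 treatment = 74

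**Effect of adjustment.** The SE is multiplied by √(1 − R²). The 95% half-width uses t = 1.993 on 74 df, or 1.994 on 70 df after four covariates. The last column applies the plan's one-observation-per-condition method, with the SD of the difference reduced to 3√(1 − R²).

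| R² (assumed) | SE | Reduction | 95% half-width | Power at n = 26, plan's method |
|---|---|---|---|---|
| 0 | 0.416 | – | 0.83 | 0.904 |
| 10% | 0.395 | 5% | 0.79 | 0.931 |
| 20% | 0.372 | 11% | 0.74 | 0.955 |
| 30% | 0.348 | 16% | 0.69 | 0.974 |

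On the four-case SE, power for 2 points is about 0.997 before any adjustment (2/0.416 = 4.8 standard errors).

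**Bias.** In a simulation of 26 surgeons and four cases each (4,000 runs per scenario; no true vest effect; subject, period and treatment in the model), a case covariate unrelated to sequence was left out. The mean estimate stayed at about 0 and type I error at 0.047 to 0.050, for R² of 0, 0.2 and 0.4. At R² = 0.2 the simulated SE was 0.412 unadjusted and 0.373 adjusted, which agrees with the formula.

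**Chance imbalance.** Between 52 vest and 52 non-vest cases, a covariate's mean difference has an SE of √(2/52) = 0.196 of its SD. If values are spread evenly over the stated ranges (assumed), the SDs are 0.577 °C and 17.3 minutes. The SEs of the imbalance are then about 0.11 °C and 3.4 minutes.

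**The case against.** The sentence on confounding explains a preference over a parallel design, and its own wording ties the reason to within-subject comparison. Read that way it is loose rather than a claim that operations are identical. Sequence is randomised, not shared with study personnel, and opened only shortly before surgery, so case factors do not confound on average. That stands.

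The plan also narrows the variation. It sets a temperature target and a scheduling window, excludes surgeons who worked the previous evening, excludes seated cases and lead gowns, and requires any helmet system to be worn in all four cases. These controls reduce between-case differences without removing them. Primary power hardly needs the gain, and variability is to be reassessed after 13 surgeons. Both points are right and limit the weight of the concern. The full analysis plan promised before data are evaluated is a natural place for the change.

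On Aim 4, the model tests only exertion and fatigue, so hours slept is never tested as an outcome. The conflict is one of definition and description.

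Two stronger readings are tempting. A reader might infer that cooling the room in no-vest cases could hide the whole 2-point difference. That needs no-vest cases held at 20 °C and vest cases at 22 °C throughout, and a slope of 1 point per °C. The documents give no slope, do not report surgeons asking for cooler rooms, and state the aim of equal temperature across a surgeon's cases.

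A reader might also infer selection bias, because in all four sequences the first two treatments determine the last two. With an assumed shift in case mix of 0.5 to 1 SD in periods 3 and 4 and R² = 0.2, the simulated bias is 0.23 to 0.48 points and type I error 0.075 to 0.199; adjustment brings the error back to about 0.05. Nothing in the documents indicates that cases would be chosen by expected allocation, so this is a possibility and not a finding.

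**Conclusion.** The concern holds as a matter of precision and definition. The design removes confounding by stable surgeon characteristics and no more. Leaving out case factors known before allocation does not bias the vest effect on average, provided that the choice of cases does not follow the expected allocation. The cost is a standard error of 0.416 where 0.395 to 0.348 might be had, a reduction of 5% to 16%. These figures rest on the plan's SD and correlation, equal correlation among the four cases, and an assumed R² of 10% to 30%. The primary test is not endangered. The benefit lies in narrower intervals and in the secondary outcomes tested at 0.017. The two definitions of perceived workload are a plain inconsistency, confined to the outcome definition and its descriptive summary.

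**What to change.** 1. In the Aim 1 to 4 models, pre-specify case covariates known before allocation is opened: procedure type, scheduled duration and hours slept. Add starting room temperature if a reading before allocation is available; the documents do not say that monitoring begins that early. Obtain the sleep report before allocation is opened.
2. Remove procedure duration and hours slept from the Aim 4 definition, so that it matches Secondary Outcome #4 (exertion and fatigue).
3. Tabulate the logged room temperature by condition, as a check on unblinded changes to the room after allocation. Do not adjust for temperature or actual duration measured after allocation, since the vest may influence them. A starting-temperature covariate would not correct for later cooling; the table is what would reveal it.
4. Reword the rationale to say that the design removes confounding by stable surgeon characteristics.

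The cost is a few sentences in the analysis plan and about 3 to 4 of 74 residual degrees of freedom, one per covariate if procedure type has two levels. Procedure type and scheduled duration are on the operating schedule, and hours slept and room temperature are already planned. The only possible new step is a room reading before allocation.
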